#### 7.2.6 PK Nights 1 and 2, Xyrem-naïve Subjects

Refer to [Section 7.1.3](#)

#### 7.2.7 Open-Label Safety Evaluation, Xyrem-naïve Subjects

- See procedures in [Section 7.4](#)

### 7.3 PSG Night Procedures for All Subjects

[Table 6](#) lists the procedures for the PSG nights by study period (Screening and End of Stable-Dose/Pre-Randomization\*) and subject population (subjects on Xyrem at study entry and Xyrem-naïve subjects). Note: \*For administrative reasons the terminology for this PSG will retain the reference to "Pre-Randomization".

For all PSG nights when subjects receive study drug, a light dinner should be taken >2 hours prior dosing. The meal should be the same or similar on all PSG nights where dosing with study drug is required. The Investigator will confirm that the light dinner planned and consumed was acceptable. The meal may be taken at the Sleep Lab or at home. No dinner restriction is required for Xyrem-naïve subjects prior to the screening PSG night.

The site will be supplied with appropriate study drug for use on Screening PSG nights. Subjects will bring the study drug dispensed to them for the End of Stable-Dose/Pre-Randomization (Xyrem-naïve subjects only) and End of Study (Part 1) PSGs.

Xyrem® (sodium oxybate) oral solution  
Clinical Study Protocol: 13-005 Amendment 5

Jazz Pharmaceuticals

---

On PSG nights, when subjects have taken study drug, subjects should be allowed to sleep after the second dose until they wake.

Ensure that subjects of driving age who received study drug during the PSG nights will not be driving themselves when leaving the sleep lab.

Xyrem® (sodium oxybate) oral solution  
Clinical Study Protocol: 13-005 Amendment 5

Jazz Pharmaceuticals

**Table 6 PSG Night Procedures**

1	2	3	4
Screening PSG		End of Stable-Dose/Pre-Randomization PSG*	End of Study (Part 1) PSG or Part 1 Early Termination a
Xyrem-naïve subjects	Subjects on Xyrem at study entry	Xyrem-naïve subjects	All subjects
Review inclusion/exclusion	Review inclusion/exclusion	No inclusion/exclusion review needed	No inclusion/exclusion review needed
No dinner restrictions	Light dinner >2 hours before dosing	Light dinner >2 h before dosing	Light dinner >2 h before dosing
Confirm parent/guardian contact information	Confirm parent/guardian contact information	Confirm parent/guardian contact information	Confirm parent/guardian contact information
No dosing	Usual nightly dose of Xyrem divided into 2 doses, 4 h apart	Nightly dose of Stable-dose Xyrem divided into 2 doses, 4 h apart	Nightly Xyrem dose taken at end of Safety Period divided into 2 doses, 4 h apart
Perform PSG	Perform PSG	Perform PSG	Perform PSG
EtCO 2 or TcCO 2 b	EtCO 2 or TcCO 2 b	EtCO 2 or TcCO 2 b	EtCO 2 or TcCO 2 b
Obtain vital signs c	Obtain vital signs d	Obtain vital signs d	Obtain vital signs d
Monitor SpO 2 e	Monitor and record SpO 2 f	Monitor and record SpO 2 f	Monitor and record SpO 2 f
Record AEs/Con Meds	Record AEs/Con Meds	Record AEs/Con Meds	Record AEs/Con Meds
---	Brief neuro exam g	Brief neuro exam g	Brief neuro exam g
No blood sample	No blood sample	The morning following the PSG, obtain fasting blood sample for GH, IGF-1, and prolactin	The morning following the PSG, obtain blood samples for 
 
◦ Fasting blood sample for GH, IGF-1, and prolactin
 
◦ Routine hematology and chemistry
 
◦ For girls <8 years of age: estradiol, FSH, and LH
 
◦ For boys <9 years of age: testosterone, FSH, and LH
 

Provide breakfast (if subject prefers to eat at the study center) in the morning after all PSG nights			

GH=growth hormone, IGF-1=insulin-like growth factor-1 (low sensitivity)

Xyrem® (sodium oxybate) oral solution  
Clinical Study Protocol: 13-005 Amendment 5

Jazz Pharmaceuticals

---

\*For administrative reasons the terminology for this PSG will retain the reference to “Pre-Randomization”.

- a) If the subject withdraws early from Part 1 of the study during the Open-Label Safety Period, perform a PSG if the subject is willing to be dosed with study drug for this PSG night. Part 1 Early termination PSG does not apply for subjects who discontinue before entering the Open-Label Safety Period.
- b) At sites where EtCO2 or TcCO2 monitoring is routinely performed.
- c) Obtain vital signs after subject has been resting for at least 5 minutes before start of PSG and prior to release from study center.
- d) Obtain vital signs after subject has been resting for at least 5 minutes at pre-dose and prior to release from study center. At 1, 4 (pre-2nd dose), 5, and 8 hours after the first Xyrem dose, heart and respiratory rates are recorded via PSG monitoring.
- e) Monitor SpO2 to determine obstructive sleep apnea status.
- f) Monitor SpO2 continuously from immediately before first dose through 8 hours after first dose, and record SpO2 pre-dose and at 1 h, 2 h, 4 h (pre-2nd dose), 5 h, 6 h, and 8 h after first dose and before release from study center while subject is awake.
- g) Brief neurological exam before discharge on the morning after the PSG.

Xyrem® (sodium oxybate) oral solution  
Clinical Study Protocol: 13-005 Amendment 5

Jazz Pharmaceuticals.

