3.1.5 Open-Label Safety Period (to allow up to 1 year Xyrem exposure)

Subjects who are eligible to participate in the Open-Label Safety Period will participate in this period for 47 weeks if they entered the study on a stable dose of Xyrem or for a period of 38-45 weeks if they entered as Xyrem naïve, depending on the duration of the titration period in which they participated (45 weeks assumes that the shortest titration period will be 3 weeks for those subjects who reach an optimal response very quickly during titration).

All study procedures and assessments will be carried out according to the planned schedule (changes in Xyrem dose will generally not affect the schedule).

All subjects will be seen in the clinic 4 weeks after the Open-Label Safety Period begins (Visit 5) and then at Weeks 18, 26, 39, and 52 from study entry (Day 1). However, if in the case of subjects who are Xyrem naïve, Visit 5 is within 2 weeks of the Week 18 visit, the first clinic visit of the Open-Label Safety Period will be the Week 18 visit.

Subjects/parent(s)/guardian(s) will be contacted in the interim by phone at Weeks 16, 22, 30, 34, 43, and 48 from study entry (Day 1). A final PSG will be performed at Week 52 or the Part 1 early termination visit (if the subject who terminates early is willing to participate in another PSG night and if they are willing to take Xyrem the evening of the PSG). The Part 1 early termination PSG does not apply for subjects who discontinue before entering the Open-Label Safety Period. Clinicians may schedule clinic or phone visits between protocol-specified clinic visits to ensure subject safety or to accommodate PK visits (if applicable). Additional drug dispensing visits may be added as required by local law or at the Investigator's discretion based on safe drug storage requirements. Stimulants for EDS may be used as adjunctive therapy throughout the trial, and can be adjusted or discontinued as appropriate.

For subjects who had entered the Double-Blind Treatment Period before Amendment 4 was effective, upon entering the Open-Label Safety Period, these subjects will be started at a dose no higher than half the Xyrem dose they received at the end of the Stable-Dose Period or the

Xyrem® (sodium oxybate) oral solution  
Clinical Study Protocol: 13-005 Amendment 5

Jazz Pharmaceuticals

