## 6.14 Removal of Subjects from the Study or Study Drug

All subjects are free to withdraw from participation in this study at any time, for any reason, and without prejudice. The Investigator must withdraw any subject from the study if the subject or subject's parent(s)/guardian(s) requests to stop participating in the study.

The Investigator, Jazz Pharmaceuticals or its designee may remove a subject from the study at any time and for any reason.

If any of the criteria below are met during the study, study drug administration must be stopped and the subject discontinued from the study.

- Suicide risk reported or assessed by C-SSRS
- Clinically significant depression independent of narcolepsy symptoms
  - If the T-score is  $\geq 65$  on CDI 2SR[S], an evaluation of depression by the Investigator (if qualified as a mental health professional) or by the Investigator in consultation with a mental health professional must be performed to exclude clinically significant depression
- Any PSG parameters that indicate, in the judgment of the Investigator, a risk to the subject's safe continued participation
- Subject becomes pregnant
- A positive urine drug screen for benzodiazepines or drugs of abuse (if the subject takes prescribed amphetamines, a positive result for amphetamines will not exclude the subject) or any suspicion by the investigator of abuse or diversion of study drug
- A positive alcohol test
- 3-fold or greater elevation above the upper limit of normal (ULN) of alanine aminotransferase (ALT) or aspartate aminotransferase (AST) accompanied by an elevation of serum total bilirubin greater than two times the ULN
- Liver enzyme (AST, ALT) value greater than or equal to 5 times the ULN
- Experiences an intolerable AE that is related to the study drug and/or procedure
- Develops any clinically significant worsening in narcolepsy symptoms during the Stable-Dose Period
- Develops a clinically significant laboratory or ECG abnormality that is related to the study drug and/or procedure
- Requires a medication that is prohibited by the protocol, with the exception of short-term opioid or benzodiazepine use (see [Section 5.7](#))
- Does not follow guidelines or procedures specified in the protocol

Xyrem® (sodium oxybate) oral solution  
Clinical Study Protocol: 13-005 Amendment 5

Jazz Pharmaceuticals

- 
- Is lost to follow-up
  - Does not continue to meet certain entry criteria or meets certain exclusion criteria during the course of the study

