  - Subject reaches his/her 18th birthday. Subjects who terminate from Part 2 of the study because they have reached 18 years of age will be considered to have completed the study.

All subjects who prematurely discontinue from the study should have all early termination assessments performed (see Section 6.14.1, Handling of Early Terminations).

The specific reason for the discontinuation should be carefully documented on the termination CRF. If assent or informed consent is withdrawn, the specific reason for withdrawing the assent or informed consent should be stated.

Adverse events resulting in termination will be followed to the satisfactory resolution and determination of outcome as ascertained by the Investigator (and/or Jazz Pharmaceuticals or its designee). The data will be recorded on the appropriate CRF.

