#### 6.14.1 Handling of Early Terminations

If a subject terminates early from the study, either at his or her request or the subject's parent(s) or guardian(s), or at the Investigator's discretion, the Investigator will record the reason(s) for early termination on the relevant CRF page and notify the Sponsor immediately. The specific reason for the withdrawal should be carefully documented on the CRF. For instance, rather than stating "withdrew informed consent," the specific reason for withdrawing the informed consent should be stated. All subjects who terminate early from Part 1 should undergo all early termination assessments in [Section 7.4.3](#). All subjects who terminate early from Part 2 should undergo all study termination assessments in [Section 7.5.5](#). Subjects who terminate from Part 2 of the study because they have reached 18 years of age will be considered to have completed the study.

It is vital to obtain follow-up data on any subject who terminated because of an AE, abnormal laboratory test, or ECG finding. In any case, every effort must be made to undertake safety follow-up procedures.

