#### 7.4.3 Visit 15 Week 52 or Part 1 Early Termination

If the subject will be continuing directly into Part 2, the Open-Label Continuation Period, see [Section 7.5](#).

- Perform a physical examination, including a brief neurological examination and a Tanner Stage Assessment ([Appendix 5](#)) but excluding a full genitourinary exam.
- Record height and weight in ordinary indoor clothes (without shoes).
- Review Cataplexy Frequency Diary.
- Review Study Drug Dosing Diary.
- Administer the following:
  - ESS (CHAD) ([Appendix 6](#))
  - SF-10 ([Appendix 7](#))
  - C-SSRS ([Appendix 8](#)) (Since Last Visit version for subjects  $\geq 12$  years of age and Children's Since Last Visit version for subjects  $< 12$  years of age)
  - CDI 2:SR[S] ([Appendix 9](#))
  - MASC-10 ([Appendix 10](#))
- Obtain vital signs (systolic and diastolic blood pressure, pulse/heart and respiratory rate, and body temperature) after the subject has been resting supine for at least 5 minutes.
- Obtain urine samples for urinalysis.
- Perform alcohol test and urine drug screens.
- Obtain urine sample for pregnancy test (only perform for female subjects who have reached menarche).
- Obtain a 12-lead ECG.
- Record all AEs on the AE CRF.
- Record all concomitant medications on the concomitant medications CRF.
- Collect study drug dispensed at the previous visit and measure compliance.
- Perform End of Study (Part 1) PSG according to the procedures for all subjects in Column 4 of [Table 6](#). If the subject withdraws early from the study during the Open-Label Safety Period, perform the PSG if subject is willing to be dosed with study drug

on this PSG night. Part 1 early termination PSG does not apply for subjects who discontinue before entering the Open-Label Safety Period.

- Obtain blood samples for the following the morning after the PSG night:
  - Fasting blood sample for GH, IGF-1, and prolactin
  - Routine hematology and chemistry
  - For girls <8 years of age: estradiol, FSH, and LH
  - For boys <9 years of age: testosterone, FSH, and LH
- If the subject will not be continuing into Part 2, record the reason why and schedule the Safety Follow-up visit.

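### The early-termination sleep study is dosed with Xyrem subject only to willingness and study period, with no exception for children whose drug Section 6.14 requires to be stopped

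*Protocol*

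**What the plan says.** Section 6.14 lists criteria and states that if any is met, "study drug administration must be stopped and the subject discontinued from the study". The list includes suicide risk, clinically significant depression, PSG findings that indicate risk, pregnancy, a positive drug or alcohol test, liver enzyme elevation, an intolerable related adverse event, and need for a prohibited medication. It also holds non-safety reasons, such as loss to follow-up.

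The same section then says: "All subjects who prematurely discontinue from the study should have all early termination assessments performed". Section 6.14.1 repeats this for Part 1, pointing to Section 7.4.3: "All subjects who terminate early from Part 1 should undergo all early termination assessments". It covers departures at the family's request and at the Investigator's discretion, and adds: "It is vital to obtain follow-up data on any subject who terminated because of an AE, abnormal laboratory test, or ECG finding".

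For a child leaving during the Open-Label Safety Period, the 7.4.3 list includes the End of Study PSG under Table 6 column 4. The dose entry in that column reads: "Nightly Xyrem dose taken at end of Safety Period divided into 2 doses, 4 h apart". The column is for all subjects and states that eligibility need not be reviewed.

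The conditions on this PSG appear in several places. Table 6 note a: "perform a PSG if the subject is willing to be dosed with study drug for this PSG night". Section 3.1.5 requires willingness to have another PSG night, and performs it "if they are willing to take Xyrem the evening of the PSG". Section 7.4.3: "perform the PSG if subject is willing to be dosed with study drug". Each adds that the PSG is not done in subjects who leave before the Open-Label Safety Period.

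**The concern.** The protocol sends children to this PSG from a section that has just required their drug to be stopped, and the PSG instructions do not say what to do about it. The cross-reference runs one way: 6.14.1 points to 7.4.3, but the PSG text never points back to 6.14. The authors did write one exception, for study period, so a site could take the list of exceptions to be complete.

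Xyrem is a central nervous system depressant and the subjects are children. A site that lets 6.14 control would skip the dose. A site working from the schedule and Table 6 could give it to a willing child stopped for safety. Sites could therefore differ in practice.

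A related gap lies outside 6.14. In other early terminations the PSG text does not ask whether dosing is safe if the child has already stopped taking the drug, and no interval between last dose and PSG is stated.

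**Working it through.** There is no figure to recompute. The check sets every statement of the early-termination PSG rule beside Section 6.14.

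**Step 1. Conditions stated in each place.**

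| Place | Willingness | Study period | Safety exception or pointer to 6.14 |
|---|---|---|---|
| Section 3.1.5 | yes | yes | none |
| Section 7.4.3 | yes | yes | none |
| Table 6 note a | yes | yes | none |
| Appendix 1.1 note p | yes | yes | none |
| Appendix 1.2 PSG note | not stated | yes | none |
| Appendix 2.2 PSG note | not stated | yes | none |
| Appendix 2.3 PSG note | not stated | yes | none |

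None mentions 6.14, an Investigator safety judgment, or interrupted dosing.

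**Step 2. Who is routed there.** Table 6 note a, Section 7.4.3 and Appendix 1.1 note p speak of a subject who *withdraws*, which suits a voluntary leaver. Section 3.1.5 speaks of one who *terminates early*, and Table 6 column 4 and Section 7.4.3 are headed for Part 1 early termination generally. Sections 6.14 and 6.14.1 cover every premature discontinuation. The word *withdraws* therefore does not reliably keep out children stopped under 6.14.

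**Step 3. Which instruction is stronger.** The stop in 6.14 is a *must*. The early-termination assessments are a *should*, and the PSG also depends on consent to dosing. The two fit together if the site does the assessments but omits the dose wherever the drug must be stopped. That is the better reading, though the site has to infer it.

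**Step 4. What is checked before the dose.** Note b of Appendix 1.2, and the matching note in Appendix 2.3, place all other visit procedures ahead of the PSG night. At this visit that puts the C-SSRS, CDI, drug, alcohol and pregnancy tests, ECG, physical examination and adverse event recording first. Chemistry is the exception: 7.4.3 and Table 6 draw it the morning after the PSG, so a liver criterion first shown by that sample could not prevent the dose.

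**Step 5. A concrete case.** Section 5.7 says a child who needs opioids or benzodiazepines for several days should be discontinued, and lets study drug be held for one night during short-term use. The protocol clearly wants to avoid giving these drugs together. Yet such a child, if willing, meets every condition stated for the dosed PSG. The same holds for a child stopped for an intolerable related adverse event.

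**The case against.** The strongest reply is that nothing conflicts. A *must* outranks a *should*, Section 11.7 tells sites to read the whole protocol and follow it exactly, and dosing a child stopped under 6.14 would breach 6.14. On that view only a cross-reference is missing. The order of procedures puts most safety checks before the dose. Section 3.1.2 lets the Investigator reduce the dose for tolerability at any time, and Sections 3.1.5 and 5.2 permit dose adjustment. Dosing is supervised (5.2), with a physician on call and a technologist present (6.8) and continuous SpO2 (6.5).

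Most of this stands and is why the point is minor. It does not remove the point. The safeguards reduce the risk of dosing but exempt nobody from it, and a paediatric safety stop should not depend on weighing verbs across sections.

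A reader might go further and infer that the protocol orders re-dosing against its own stopping rule. It does not, because the mandatory stop can be read as controlling throughout.

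A reader might also set the full last dose against the half-dose restart limit in 3.1.5 and call it an excessive restart. The documents do not support that. The limit applies to every pre-Amendment 4 subject leaving the blinded period, including those who stayed on Xyrem, and so is not a general rule for interruptions. Section 5.7 allows a one-night hold without stating a reduced restart. Section 3.1.8 leaves titration after less than one month off drug to Investigator judgment.

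**Conclusion.** The point holds as a minor safety clarification. The PSG text carries no exception for children stopped under 6.14 and does not address interrupted dosing in other early leavers. Followed alone, it would allow a willing child stopped for safety to be dosed again.

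Its size cannot be put as a number. The protocol gives no rate of safety stops during the Open-Label Safety Period and no interval between last dose and PSG, so the number of children affected could be none. No ratio of doses or blood levels is a fair measure of the risk.

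The conclusion assumes that some sites would work from Table 6 or the schedule without returning to 6.14. If every site lets 6.14 control, only the interruption gap remains, and there Investigator discretion over dose already helps. Efficacy is unaffected, since this PSG falls after the randomized comparison and serves safety.

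**What to change.** In Section 7.4.3 and Table 6 note a, add two statements:

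- The dosed early-termination PSG is not performed in a subject who was discontinued for a Section 6.14 safety criterion, or who is found at that visit to meet one. Name the criteria that count, because the 6.14 list also contains non-safety reasons.
- In any other early termination it is performed only if the Investigator judges dosing at that dose to be safe, including after any interruption of study drug.

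Have Section 3.1.5 and the PSG notes in Appendices 1.1, 1.2, 2.2 and 2.3 point to that text.

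The cost is two sentences and a few cross-references. A few early-termination PSGs would be lost, from children whose respiratory data on drug may be of interest.

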## 7.4 Open-Label Safety Period for All Subjects

A Schedule of Events for subjects in the Open-Label Safety Period is in [Appendix 1.1](#) for subjects on Xyrem at study entry and in [Appendix 2.2](#) for subjects who are Xyrem-naïve at study entry.

### 7.4.1 Visit 5 (4 weeks after end of the Double-Blind Treatment Period) and Visits 7, 9, 12 (Weeks 18, 26, 39 from Day 1)

- Record height and weight in ordinary indoor clothes (without shoes).
- Obtain vital signs (systolic and diastolic blood pressure, pulse/heart and respiratory rate, and body temperature) after the subject has been resting for at least 5 minutes.
- Perform urine drug and alcohol test screens.
- Review Cataplexy Frequency Diary.
- Review Study Drug Dosing Diary.
- Administer the following:
  - ESS (CHAD) ([Appendix 6](#))
  - SF-10 ([Appendix 7](#))
  - C-SSRS ([Appendix 8](#); Since Last Visit version for subjects  $\geq 12$  years of age and Children's Since Last Visit version for subjects  $< 12$  years of age)
  - CDI 2:SR[S] ([Appendix 9](#))
  - MASC-10 ([Appendix 10](#))
- Record all AEs on the AE CRF.
- Record all concomitant medications on the concomitant medications CRF.
- Collect study drug dispensed at the previous visit and measure compliance.
- Dispense study drug. (Access IVRS/IWRS.) Provide instructions for dose administration and, if flavored diluent is requested and available, the preparation of study drug with flavored diluent to subjects/parent(s)/guardian(s). See [Section 6.10](#).
- Schedule the next clinic or phone visit

